The primary goal of the phase Ib study is to assess the tolerability and safety of the combination therapy. Once the highest tolerable dose is identified or the clinical doses of imatinib (400 mg daily) and BGJ398 (125 mg qd – three weeks on and one off) are reached, the phase II portion of the study will be initiated. The primary endpoint of the phase II portion is to assess Response Rate (RR) (complete response (CR) + partial response (PR)) by RECIST 1.1.

The phase Ib portion of the study will be performed in standard 3+3 fashion. The phase Ib portion of the study will be open to all patients with locally advanced or metastatic GIST who have progressed on imatinib. An initial cohort of three eligible patients with locally advanced or metastatic GIST will initiate treatment with BGJ398 at 75 mg daily (three weeks on and one off) and imatinib at 400 mg daily for 4 weeks (1 cycle). Depending on the toxicity, dose levels of imatinib (400 mg daily) + BGJ398 will be investigated as outlined below (Table 1). As imatinib 400 mg PO QD is standard of care for metastatic GIST, this dose will remain constant (barring individual dose modifications outlined in section 9.2a).

Table 1: The dose escalation schema:

Dose Level	Imatinib	BGJ395
-2	400mg daily	25 mg qd

MEMORIAL SLOAN-KETTERING CANCER CENTER
IRB PROTOCOL

[figure not shown]
IRB#: 14-140 A (7)

-1	400 mg daily	50 mg qd
1	400 mg daily	75 mg qd
2	400 mg daily	100 mg qd
3	400 mg daily	125 mg qd

Any adverse event that meets criteria in section 9.1 that occurs prior to the second cycle (i.e. before C2D1) will be considered a Dose Limiting Toxicity (DLT) for the purposes of dose escalation to the next dose level. Any adverse event that occurs after the first cycle may require a dose reduction for the patient but will not impact the assessment of dose level safety.

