**MEMORIAL SLOAN-KETTERING CANCER CENTER
IRB PROTOCOL**

IRB#: 14-140 A (7)

The first three patients will be enrolled at Dose level 1 (Table 1, see section 1) using treatment schedule A. Dose level 1 is chosen based on the standard of care imatinib dose of 400 mg daily in the advanced GIST patient population, and an intermediate dose level of BGJ398 (75 mg daily). This dose is below the BGJ398 MTD of 125 mg daily identified in phase I trials as monotherapy. BGJ398 dose level 1 to -2 will be administered using a schedule of BGJ398 taken daily for 3 weeks followed by one week off and imatinib taken daily throughout the 4 week cycle period (treatment schedule A).

The maximum pace of dose escalation within each cohort is outlined in Table 2. Expansions of lower dose levels may be made based on safety and tolerance considerations at the MSKCC Principal Investigator's discretion, and the selected RP2D may be lower than the MTD defined below. If dose level 1 is not found to be tolerable, then the next cohort will be enrolled at dose level -1. If dose level -1 is not found to be tolerable, then the next cohort will be enrolled at dose level -2. If dose level -2 is not found to be tolerable, then the study may be terminated based on discussions with the MSKCC Principal Investigator. If 0-1 of 6 patients experience a DLT on dose level 3, this will be the RP2D.

Table 2:

Number of Patients with DLT at a Given Dose Level	Escalation Decision Rule
0 out of 3	Enter 3 patients at the next dose level.
1 out of 3	Enter at least 3 more patients at this dose level. 
 • If 0 of these additional 3 patients experience DLT (1/6 total), proceed to the next dose level. • If 1 or more of this group suffer DLT ($\geq 2/6$ total), then dose escalation is stopped, and this dose is declared the MTD. Three (3) additional patients will be entered at the next lowest dose level if only 3 patients were treated previously at that dose.
≥ 2	Dose escalation will be stopped. This dose level will be declared the MTD. Three (3) additional patients will be entered at the next lowest dose level if only 3 patients were treated previously at that dose.
≤ 1 out of 6 at highest dose level below the MTD	This is generally the recommended phase 2 dose. At least 6 patients must be entered at the recommended phase 2 dose (RP2D).

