Using treatment schedule A, if dose level 1 to -2 is identified as the MTD and concern exists regarding therapeutic activity of BGJ398 at this dose level, expansions with higher dose levels (1 to 3) may be considered at the MSKCC PI's discretion, with modification of the treatment schedule. In this setting BGJ398 will be administered daily for one week followed by 3 weeks off and imatinib will be taken

**MEMORIAL SLOAN-KETTERING CANCER CENTER
IRB PROTOCOL**

IRB#: 14-140 A (7)

daily throughout the 4 week cycle period (treatment schedule B). The higher dose level expansion will start by enrolling 3 patients into a cohort, at dose level 1, using treatment schedule B.

When using treatment schedule B the maximum pace of dose escalation within each cohort is outlined in Table2.

Upon documentation of the RP2D dose and treatment schedule of the combination, the phase II trial will open and all subsequent patients enrolled will initiate treatment at that dose and treatment schedule with any subsequent dose modifications as outlined below.

Toxicity will be assessed using the NCI CTCAE (version 4.03) unless otherwise specified. Dose Limiting Toxicity (DLT) is defined as an unexpected adverse event (AE) or abnormal laboratory value assessed as at least possibly related to the study medication, which occurs ≤ 28 days (1 cycle) following the first dose of BGJ398 (cycle 1), and meets any of the criteria listed in Table 3. Please note plasma assessments may substitute for serum assessments per local laboratory standards.

Table 3: Criteria for defining dose-limiting toxicities

TOXICITY	DLT CRITERIA
Hematology	CTCAE grade 4 neutropenia lasting more than 7 consecutive days
	CTCAE grade 4 thrombocytopenia
	CTCAE Grade 3 or 4 neutropenia with fever (temperature $\geq 38.5^{\circ}\text{C}$)
Skin and subcutaneous tissue disorders	Rash, HFSR (Hand Foot Skin Reaction) or photosensitivity CTCAE Grade 3 > 7 consecutive days despite skin toxicity treatment (as per local practice)
	Rash, HFSR or photosensitivity CTCAE Grade 4
Eye disorders	CSR (Central Serous Retinopathy) CTCAE Grade 2 for > 14 consecutive days confirmed by ophthalmologic examination
	CSR (Central Serous Retinopathy) CTCAE Grade ≥ 3 , confirmed by ophthalmologic examination
	Retinal disorder other than CSR (retinal detachment/tear, retinal vascular disorder, retinopathy other) CTCAE Grade ≥ 2 confirmed by ophthalmologic examination

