	Visual disturbances without ocular (retinal) changes: Blurred vision, Flashing lights, Floaters, Corneal abnormalities CTCAE Grade ≥ 3
Gastro-intestinal	\geq CTCAE grade 3 nausea or vomiting ≥ 48 hrs despite optimal anti-emetic therapy
	\geq CTCAE grade 3 diarrhea ≥ 48 hrs despite optimal anti-diarrhea treatment
	Pancreatitis \geq CTCAE grade 3
Hepato-biliary	\geq CTCAE grade 3 total bilirubin
	\geq CTCAE grade 3 ALT (isolated increases in AST without concomitant increases

**MEMORIAL SLOAN-KETTERING CANCER CENTER
IRB PROTOCOL**

IRB#: 14-140 A (7)

	in ALT will not be considered dose-limiting, because of the non-specific nature of AST)
	Serum alkaline phosphatase CTCAE Grade 4 > 7 consecutive days
Investigations (Metabolic)	Serum Lipase and/or serum amylase (asymptomatic) CTCAE grade 3 for > 7 consecutive days Serum Lipase and/or serum amylase (asymptomatic) CTCAE grade 4 Symptomatic serum lipase and/or serum amylase ≥ CTCAE grade 3
ECG QT Interval	QTcF interval ≥ 501 ms on at least two separate ECGs
Renal	Serum creatinine > 2x ULN Serum Phosphorous that requires dose interruption of BGJ398 for >14 days of first 21 days of Cycle 1
Non-hematologic events	≥ CTCAE grade 3, except for the exclusions noted below
Exceptions to DLT criteria	Grade 3 alopecia
	< 5 days of CTCAE grade 3 fatigue
	< 5 days of CTCAE grade 3 edema
	Grade 3 laboratory abnormalities that are responsive to oral supplementation or deemed by the investigator to be clinically insignificant
CTCAE version 4.03 will be used for all grading. Optimal therapy for vomiting or diarrhea will be based in institutional guidelines, with consideration of the prohibited medications listed in this protocol.	

Phase II: The RP2D doses and treatment schedule defined in the phase Ib clinical trial will be used to conduct the phase II portion of the study.

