Following resolution of toxicity to baseline or \leq grade 1, treatment is resumed at either the same or lower doses of study drugs as per the criteria in Table 6. If treatment is resumed at the same doses of study drugs, and the same toxicity recurs with the same or worse severity regardless of duration, doses must be reduced to the next lower dose level (Table 6). If treatment is resumed at the lower doses of study drugs, and the same toxicity recurs with the same or worse severity, the patient must discontinue study treatment unless a continuation is allowed in discussion with the MSKCC PI.

If a patient requires a dose delay of > 14 consecutive days of BGJ398 from the intended day of the next scheduled dose, then the patient should be discontinued from the study treatment unless a continuation is allowed in discussion with the MSKCC PI.

In exceptional situations, study treatment may continue even if the patient experienced one of the treatment stopping rules. The decision to allow for continuation of treatment will be made on a case-by-case basis following discussion between the MSKCC Principal Investigator (MPI) and the Investigator. Situations that may allow for continuation of treatment include but are not limited to the following. A dose delay of > 14 days has occurred, but the patient is clearly benefiting from study treatment (i.e., stable disease, partial response, or complete response) and it is the investigator's opinion that no safety concerns are present, after discussion with the MPI, the patient may remain on the study treatment. A third or subsequent reduction (to dose level -3) in dose may be allowed if the patient is clearly benefiting from study treatment (i.e., stable disease, partial response, or complete response) but is experiencing adverse events that prevent continued treatment at the already reduced dose.

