For guidance regarding interruptions in BGJ398 therapy due to adverse events, please see Table 7. Of special note is management of hyperphosphatemia, an expected on-target drug effect. See the Renal section of Table 8 for dose interruptions for acute kidney injury accompanied by hyperphosphatemia. Recommendations for prophylaxis and dose modifications for hyperphosphatemia are outlined in Table 8. Exact timing of stopping/starting BGJ398 in the setting of elevated phosphorous levels will be left to the judgment of the treating physician, and differences in phosphate management will not be considered protocol deviations. A list of high-phosphorous foods and suggested alternatives is provided in Appendix F to guide discussions regarding appropriate dietary intake. Please note plasma assessments may substitute for serum assessments per local laboratory standards.

MEMORIAL SLOAN-KETTERING CANCER CENTER
IRB PROTOCOL

IRB#: 14-140 A (7)

Table 6: Dose reduction table

Dose level	BGJ398	
Dose level 0	RP2D	Starting dose
Dose level -1	RP2D minus 25 mg	
Dose level -2	RP2D minus 50mg	
Dose level -3	RP2D minus 75mg	Allowed only if patients is clearly benefiting from study treatment, but is experiencing AE that prevent continued treatment at dose level -2 and applicable based on RP2D

Table 7: Criteria for interruption and re-initiation of BGJ398 treatment

Worst Toxicity CTCAE using the current active CTCAE version	Recommended Dose Modifications any time during a cycle of therapy
Cardiac disorders	
Cardiac - Prolonged QTc interval by Fridericia's Formula (QTcF)	
Grade 1 and 2 : QTcF 481-500 msec (asymptomatic)	Maintain dose level of BGJ398 
 ECG assessments should be performed for 2 additional cycles at the same frequency as in cycle 1, or as clinically indicated. If ECG assessments show no QTcF \geq 481 msec, for subsequent cycles ECG monitoring will be performed as per visit schedule. If ECG assessments are still abnormal (QTcF \geq 481 msec and \leq500 msec), then ECG monitoring must continue at the same frequency as in cycle 1 for all subsequent cycles.

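### Table 7 recommends stopping BGJ398 permanently for at least four cycle-1 toxicities that Table 3 does not score as dose-limiting, so the 3+3 count can treat such a patient as having no DLT (minor)

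*Combined protocol and SAP*

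**What the plan says.** **What is a DLT.** Section 9.1 requires an unexpected, at least possibly related event or laboratory value within 28 days "following the first dose of BGJ398 (cycle 1), and meets any of the criteria listed in Table 3". Section 1.0 gives no second route: "Any adverse event that meets criteria in section 9.1 that occurs prior to the second cycle" is what counts for escalation. Table 3 has specific rows, including neutropenia ("CTCAE Grade 3 or 4 neutropenia with fever", with a temperature of at least 38.5 C) and the eye ("Retinal disorder other than CSR (retinal detachment/tear, retinal vascular disorder, retinopathy other", from Grade 2). It also has a general non-hematologic row that starts at "CTCAE grade 3, except for the exclusions noted below".

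**When BGJ398 is stopped.** Table 7 in Section 9.3.2 sets out holds, reductions and permanent stops. Its action column is headed "Recommended Dose Modifications any time during a cycle of therapy", so it covers cycle 1.

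**Who is counted.** Table 2 decides on the number of patients with a DLT at the dose level. Section 14 (Phase 1b) replaces patients who stop before Cycle 2 Day 1 for reasons other than toxicity.

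**Where discretion enters.** Section 9.1 says "The maximum pace of dose escalation within each cohort is outlined in Table 2". Sections 9.1 and 14 let the principal investigator choose a recommended phase II dose (RP2D) below the MTD. Section 9.3.2 says that, exceptionally, "study treatment may continue even if the patient experienced one of the treatment stopping rules".

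**The concern.** DLT criteria and dose-modification rules are written for different purposes and need not agree line by line. Here, though, they disagree in a direction that matters for dose finding. A related cycle-1 toxicity can be serious enough for Table 7 to end BGJ398 and still leave no mark on the escalation count. Because the patient stopped for toxicity, Section 14 does not replace them. They remain in a denominator of 3 or 6 and contribute to the evidence that the level is tolerable.

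Two of the four events are ones the protocol looks for inside the DLT window: Table 9 schedules an eye examination and an echocardiogram or MUGA scan in week 4 of cycle 1. All phase II patients start at the RP2D, so a permissive count would carry forward.

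**Working it through.** **Step 1. Set each Table 7 stop beside Table 3.** The liver grade limits are those printed in Table 7 (ALT Grade 3 is >5 x ULN; bilirubin Grade 3 is >3 x ULN).

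| Event, cycle 1, at least possibly related | Table 7 | Table 3 | Scored? |
|---|---|---|---|
| Congestive heart failure, Grade 2 | Discontinue | No heart-failure row; general row starts at Grade 3 | No |
| Grade 3 febrile neutropenia, fever below 38.5 C, unresolved at 7 days | Discontinue; fever means one reading >38.3 C or at least 38.0 C for over one hour | Needs at least 38.5 C; general row is non-hematologic only | No, unless the neutropenia is Grade 4 for over 7 days, which has its own row |
| AST or ALT >3-5 x ULN with bilirubin >2-3 x ULN, no liver metastasis or liver progression, over 7 days to resolve | Discontinue | ALT and bilirubin only from Grade 3 | No |
| Retinal vein occlusion, Grade 1 | Discontinue | Non-CSR retinal disorder only from Grade 2 | No |

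None of the four is among Table 3's listed exceptions (alopecia, short fatigue or edema, certain Grade 3 laboratory values) or its separate exemption for isolated AST rises.

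**Step 2. Follow the patient through the counting rules.** No Table 3 criterion is met, so there is no DLT. The stop was for toxicity, so there is no replacement. Table 2 counts DLTs only, so the patient adds 1 to the denominator and 0 to the numerator.

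**Step 3. Effect on one decision, with no rate assumed.** One uncounted patient is 1/3 = 33% or 1/6 = 17% of the deciding cohort.
- 1/3 (enter three more) becomes 0/3 (next level permitted).
- 2/6 (stop) becomes 1/6 (next level permitted).
- The next level is 25 mg higher: 100/75 - 1 = 33%, or 125/100 - 1 = 25%.
- At dose level 3, 1/6 in place of 2/6 makes 125 mg the RP2D unless a lower dose is chosen.

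**Step 4. How often?** The documents give no combination data. In the BGJ398 monotherapy study (Section 11.1.2.1, 94 patients, all cycles), suspected cardiac failure was 1/94 = 1.1%, and that case was Grade 3/4, so 0/94 were below Grade 3 under that term. Febrile neutropenia does not appear in the rows available for this review. The exact one-sided 95% upper bound for 0/94 is 1 - 0.05^(1/94) = 3.1%. The available rows of Table 13 each contain at least one Grade 3/4 event, so the table gives no rate for a Grade 1 retinal vein occlusion or the combined liver signal. None of the six adverse-event discontinuation causes named in that section matches the four events, although ten such discontinuations are reported.

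**Step 5. Operating characteristic over an assumed range.** The plan states no operating characteristic for the 3+3, so there is nothing to reproduce. From Table 2, with p the chance that a patient counts as a DLT,

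P(escalation permitted) = (1-p)^3 + 3p(1-p)^2 x (1-p)^3.

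Let d be the Table 3 DLT rate and h the rate of uncounted stops, taken as separate patients. Both are assumptions. The plan as written uses p = d; counting the stops uses p = d + h.

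| d | As written | h = 1% | h = 5% | h = 10% | h = 20% |
|---|---|---|---|---|---|
| 10% | 0.906 | 0.889 | 0.814 | 0.709 | 0.494 |
| 17% | 0.773 | 0.752 | 0.665 | 0.557 | 0.360 |
| 25% | 0.600 | 0.578 | 0.494 | 0.396 | 0.234 |

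At h = 1% the difference is about 0.02 (for d = 17%, 0.773 - 0.752 = 0.021); at h = 5% it is about 0.1 (0.773 - 0.665 = 0.108). The monotherapy data give no support for the right-hand columns.

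**The case against.** The best case against the point has four parts.

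- **It is a design choice.** Table 3 departs from Table 7 on purpose elsewhere: isolated AST rises are declared not dose-limiting, although Table 7 stops treatment at Grade 4 AST. This stands for AST. It does not reach the four events, for which no exemption is written.
- **No sentence says these patients are DLT-free.** Correct; it is an inference. But Section 14's replacement rule and Table 2's count leave no other place to put them.
- **Discretion covers it.** Table 7's actions are recommendations, a stop can be waived, Table 2 is a maximum pace and the RP2D may be set lower. All true, and it limits the consequence. It does not change the number of DLTs recorded.
- **The evidence is thin.** No instance of the four events is shown. The monotherapy data were graded under CTCAE v3.0, whereas this trial uses 4.03. The CTCAE text is not in the documents, so how Grade 1 retinal vein occlusion or Grade 2 heart failure would be assigned cannot be checked; the table above relies on Table 7's own use of those grades. This stands, and it keeps the point minor.

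A reader might infer that every toxicity-driven stop, including those under Table 8, should be a DLT. The documents do not support that. Table 3 has its own phosphate rule: interruption for more than 14 of the first 21 days. If BGJ398 is held from Day 10 and phosphate does not come down, Table 8 stops it at about Day 10 + 14 = Day 24, with only Days 10-21, or 12 days, interrupted. Scoring that stop would override the phosphate rule for the commonest suspected event (hyperphosphataemia, 61.7% in Table 13). A rule tied to recommended, waivable stops would also score identical events differently between patients.

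**Conclusion.** The gap is real and minor. At least four cycle-1 toxicities that lead to a recommended permanent stop are not DLTs under Table 3, and by direct inference those patients remain in the cohort without a DLT. *At least* is deliberate: creatinine >1.5-2.0 x ULN with a calcium-phosphate product above 55 may be a further case, but the row alignment in that part of Table 7 is uncertain in the text available, so it is left out.

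Two stronger readings are not supported. One is that the miscount forces escalation; Table 2 sets only a maximum pace, so escalation is permitted, not compelled. The other is that the RP2D will be too high; that would need a rate for these events on the combination, which the documents do not give. The decision-level effect (1/3 to 0/3, or 2/6 to 1/6) needs no assumed rate. Its frequency is unknown and probably low.

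**What to change.** Add fixed event criteria to Table 3, cross-referenced in Section 14, rather than a rule tied to discontinuation. Score as DLTs, when at least possibly related and with onset within 28 days of the first BGJ398 dose:

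- (a) congestive heart failure of Grade 2 or higher;
- (b) retinal vein occlusion of any grade;
- (c) AST or ALT >3 x ULN with total bilirubin >2 x ULN, without liver metastasis or liver progression, not resolved to Grade 1 or lower within 7 days;
- (d) Grade 3 or 4 neutropenia with fever as Table 7 defines it (one reading >38.3 C, or at least 38.0 C sustained for more than one hour), not resolved within 7 days, in addition to the existing 38.5 C row.

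State that these rows apply whether or not the event is listed as expected for reporting. Section 9.1 asks for an unexpected event without saying against which list, and Table 16 lists cardiac failure as expected. Leave the phosphate rule, the isolated-AST exemption and the other exceptions unchanged, and do not refer to Table 8.

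Cost: one amendment to one table and a cross-reference, with no new visits, tests or data. Slightly more events count as DLTs, escalation may stop one level earlier, and a cohort decision may wait up to 7 days when onset is late in the cycle.

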9.2 Follow-up for toxicities

Patients whose treatment is interrupted or permanently discontinued due to an adverse event or clinically significant laboratory value must be followed until resolution or stabilization of the event. Appropriate clinical experts (e.g. ophthalmologist, cardiologist, dermatologist) should be consulted as deemed necessary. A dose interruption of ≥ 28 days may require the patient to be discontinued from the study (with the exception of patients who undergo surgery; see section 13). Patients will continue to be followed for toxicity for 28 days following the last dose of study medication.

Patients exhibiting hypomagnesaemia, hypocalcaemia, and/or hypokalemia, should receive electrolyte replacement as indicated by national and institutional guidelines and be followed until laboratory values have normalized or as clinically indicated.

Patients on the study will be examined regularly to monitor for the possible development of CSR, as the appearance of CSR has been associated with BGJ398 treatment. Patients will receive an ophthalmological visit at baseline and 4 weeks after initiation of the study drug. If an ocular event occurs, patients will undergo ophthalmological evaluation as mandated by the study ophthalmologist. For patients developing a CSR of any grade it is recommended to follow up the CSR with an ophthalmological exam every two weeks for 8 weeks, and subsequently at approximately a 4-

MEMORIAL SLOAN-KETTERING CANCER CENTER
IRB PROTOCOL

IRB#: 14-140 A (7)

week interval. Dose adjustments for ocular toxicities are outlined in Table 11. If ocular findings re-develop after rechallenge with drug, drug may be permanently discontinued based on evaluation by the study ophthalmologist.

All patients will have baseline cardiac ejection fraction evaluated by echocardiogram or MUGA studies. If a cardiac event occurs, the patients will undergo cardiac evaluation as seen appropriate by the investigator.

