Grade 3 : QTcF > 500msec as identified on the ECG by the investigator	
 Hold BGJ398. Monitor patient with hourly ECGs until the QTcF has returned to baseline. Perform further monitoring as clinically indicated. Exclude other causes of QTcF prolongation such as hypokalemia, hypomagnesaemia and decreased blood oxygenation. Patients should receive appropriate electrolyte replacement and should not receive further BGJ398 until electrolytes are documented to be within normal limits. 
Once the QTcF prolongation has resolved, patients may be re-treated at one lower dose level at the investigator's discretion

MEMORIAL SLOAN-KETTERING CANCER CENTER
IRB PROTOCOL

IRB#: 14-140 A (7)

Worst Toxicity CTCAE using the current active CTCAE version	Recommended Dose Modifications any time during a cycle of therapy
	
 • ECG assessments should be performed for 2 additional cycles at the same frequency as in cycle 1 or as clinically indicated 
 ○ If ECG assessments show no QTcF \geq 481 msec, for subsequent cycles ECG monitoring will be performed as per visit schedule. ○ If ECG assessments are still abnormal (QTcF \geq 481 msec and \leq500 msec), then ECG monitoring must continue at the same frequency as in cycle 1 or as clinically indicated, for all subsequent cycles • Patients who experience recurrent QTcF \geq 500msec after one dose reduction will be discontinued from study. 
NB: If ventricular arrhythmia or Torsades de Pointes is observed in a patient, he/she will be discontinued from the study.
 
Whenever QTcF \geq 501msec is observed, a plasma sample for determination of BGJ398 concentration should be obtained with the time of sample collection noted.

Cardiac disorders - others Grade \geq 3, or congestive heart failure \geq 2	Discontinue patient from study treatment.
Investigations-Hematology	
ANC decreased (Neutropenia) Grade 3 (ANC $<$ 1.0 - 0.5 x 10 ⁹ /L) Grade 4 (ANC $<$ 0.5 x 10 ⁹ /L)	Hold dose of BGJ398 until resolved to CTCAE Grade \leq 1 or baseline, then 
 • If resolved in \leq 7 days, maintain dose level of BGJ398 • If resolved in $>$ 7 days, \downarrow 1 dose level of BGJ398. Hold dose of BGJ398 until resolved to CTCAE \leq Grade 1, \downarrow 1 dose level of BGJ398.

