9.4.3 Prohibited concomitant therapy with BGJ398

CYP inhibitors

Strong inhibitors of CYP3A4 such as the ones listed in Appendix C are prohibited because BGJ398 is a likely substrate of this isoenzyme. Caution should be used during administration of moderate inhibitors. The following food products are prohibited: Seville oranges or juice, grapefruit, grapefruit juice, grapefruit hybrids, and pummelos.

CYP inducers: Strong inducers of CYP3A4 are prohibited because their usage would likely decrease the exposure of BGJ398. Therefore, agents such as those listed in Appendix E are prohibited. Caution should be used during administration of moderate inhibitors.

MEMORIAL SLOAN-KETTERING CANCER CENTER IRB PROTOCOL

IRB#: 14-140 A (7)

Phosphorus and calcium: Medications that increase the serum levels of phosphorus and/or calcium are prohibited. These include, but are not limited to, calcium, phosphate, vitamin D, parathyroid hormone (PTH).

Herbal medications: Herbal preparations/medications are not allowed throughout the study. These herbal medications include, but are not limited to: St. John's wort, Kava, ephedra (ma huang), ginkgo biloba, dehydroepiandrosterone (DHEA), yohimbe, saw palmetto, and ginseng. Patients should stop using these herbal medications 7 days prior to first dose of study drug.

Enzyme Inducing Anti-epileptic drugs (EIAEDs): Enzyme inducing anti-epileptic medication is not allowed (please refer to Appendix E). Patients who were previously on a non-EIAED and need to permanently change anticonvulsants, but who cannot change to another non-EIAED must be discussed with the MSKCC PI and Novartis. These patients will be taken off-study unless it is felt that they have benefited from the therapy following discussion with the MSKCC PI and Novartis.

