Appendix F: List of prohibited medications with BGJ398

List of CYP3A inhibitors and inducers that are prohibited
Table 14-2 List of prohibited medication while on study

Category	Drug Names
Strong inducers of CYP3A4	Avasimibe, carbamazepine, phenobarbital, phenytoin, rifabutin, rifampin, St. John's wort
Strong Inhibitors of CYP3A4	Clarithromycin, conivaptan, indinavir, itraconazole, ketoconazole, voriconazole, lopinavir, mibefradil, nefazodone, nelfinavir, posaconazole, ritonavir, saquinavir, telithromycin, grapefruit juice, juice from Seville oranges
Medications which increase serum phosphorus and/or calcium	Calcium, phosphate, vitamin D, parathyroid hormone (PTH)

EIAEDs that are prohibited

Strong CYP3A inducers	Moderate CYP3A inducers
carbamazepine	felbamate
phenobarbital	topiramate (>200 mg/day)
phenytoin	oxcarbazepin
fosphenytoin	eslicarbazepin
primidone	rufinamide

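### Section 9.2 directs replacement for hypocalcaemia, and Table 7 directs electrolyte replacement after QTcF prolongation, while Section 9.4.3 and Appendix F prohibit calcium on study with no exception

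*Combined protocol and SAP*

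**What the plan says.** Two places point towards replacement.

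- Section 9.2 names low calcium directly: "Patients exhibiting hypomagnesaemia, hypocalcaemia, and/or hypokalemia, should receive electrolyte replacement as indicated by national and institutional guidelines". Follow-up continues until values are normal or as clinically indicated.
- Table 7 (Section 9.3.2), in the row for QTcF above 500 msec, says: "Patients should receive appropriate electrolyte replacement and should not receive further BGJ398 until electrolytes are documented to be within normal limits".

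Two places prohibit it.

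- Section 9.4.3: "Medications that increase the serum levels of phosphorus and/or calcium are prohibited". Calcium and vitamin D are among the agents it then names.
- Appendix F repeats those agents in a table headed "List of prohibited medication while on study".

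Table 3 (Section 9.1) adds a rule that may depend on the answer. Among the exceptions to the DLT criteria it lists "Grade 3 laboratory abnormalities that are responsive to oral supplementation or deemed by the investigator to be clinically insignificant".

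**The concern.** Section 9.2 and Section 9.4.3 give opposite instructions for the same patient, and neither refers to the other. The situation can be foreseen. Section 11.1.1 includes hypocalcemia among events reported on imatinib trials, with the relationship to imatinib undetermined. Calcium is in the chemistry panel, which Tables 9 and 11 schedule weekly in cycle 1, so low values will be seen and sites will have to choose.

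The main stake is safety: a deficiency is either treated or left untreated in patients who are also monitored for QT prolongation. A lesser stake is consistency between sites in when BGJ398 is restarted and, in a narrow case, in what counts as a DLT in phase Ib.

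**Working it through.** No figure in the plan bears on this point, so the check is a comparison of the passages.

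**1. Can one course of action satisfy both sections?** Section 9.2 requires replacement when calcium is low. Section 9.4.3 defines its ban by effect, covering whatever raises serum calcium, and then names agents as examples. Effective replacement raises serum calcium, so no choice of product meets both rules.

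**2. Is there an exception elsewhere?**

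- Section 9.4 opens by permitting supportive care, but only in general terms. It does not mention calcium or override the specific prohibition in 9.4.3.
- Holding BGJ398 does not clearly lift the ban, because Appendix F applies it for the whole time on study.
- The note closing Table 3 makes guideline-based treatment of vomiting and diarrhea subject to the prohibited list. Section 9.2 has no such clause.
- Section 9.3.2 says that differences in phosphate management are not protocol deviations. Nothing comparable covers calcium.

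**3. Restart after QTcF prolongation.** Table 7 gives potassium and magnesium as examples of causes to exclude, but its restart condition covers electrolytes generally. When calcium is low, Table 7 asks for replacement and 9.4.3 forbids it. A site that gives precedence to 9.4.3 may not reach the restart condition. A BGJ398 delay of more than 14 days then leads to stopping, unless continuation is agreed with the MSKCC principal investigator (Section 9.3.2 and the note ending Table 7).

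**4. DLT status.** All of the following must hold before the conflict can matter:

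- phase Ib, cycle 1;
- hypocalcaemia of Grade 3 exactly, since lower grades do not meet the general non-hematologic criterion and the laboratory exception does not extend to Grade 4;
- the value is unexpected and at least possibly related to study medication (DLT definition, Section 9.1);
- the investigator has not judged it clinically insignificant, which is the second limb of the exception.

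In that case a site that replaces calcium by mouth can show a response and exempt the value. A site that observes the ban cannot.

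**5. What one reclassified patient does under Table 2.**

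| DLT count if exempt | DLT count if not exempt | Change in decision |
|---|---|---|
| 0 of 3 | 1 of 3 | escalate becomes enter at least 3 more |
| 1 of 3 | 2 of 3 | enter at least 3 more becomes stop |
| 1 of 6 | 2 of 6 | proceed becomes stop |

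**6. How often?** No rate of hypocalcaemia is given. For BGJ398 alone, the readable rows of Table 13 show hypercalcaemia in 5 of 94 patients (5/94 = 5.3%) and no row for hypocalcaemia; part of that table is not available. Table 16 lists hypercalcaemia but not hypocalcaemia. Section 6.2 excludes uncontrolled disorders of calcium and phosphate. These are monotherapy data and do not rule the event out in combination, but they suggest that the case in step 4 is rare.

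**The case against.** The best defence is that the practical consequences are limited. Much of that defence stands, and it rules out several stronger readings that a reader might infer.

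- *That Table 7 traps a hypocalcaemic patient.* Its sentence itself calls for replacement, so it is a second instruction on the side of 9.2. The obstacle comes from 9.4.3 and Appendix F.
- *That any site giving calcium commits a prohibited-medication violation.* Section 16.3.2 defines a violation as an unapproved departure from the protocol. Following an express instruction in 9.2 is not plainly a departure, so the status of such treatment is unclear.
- *That DLT status can switch for every affected phase Ib patient.* It can do so only under the joint conditions in step 4. It is also open to question whether an event already listed for imatinib in Section 11.1.1 is unexpected.
- *That the same split arises for phosphate.* Section 9.2 does not name low phosphate, so it sets up no conflict with 9.4.3 there.

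One could also argue that 9.4.3 is aimed at raising calcium that is already normal. That may be its intent, but neither 9.4.3 nor Appendix F says so. None of these points removes the direct conflict over low calcium.

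**Conclusion.** The contradiction is real and follows from the current text alone: 9.2 and Table 7 on one side, 9.4.3 and Appendix F on the other. Management of low calcium, and restart of BGJ398 when calcium is low after QTcF prolongation, depend on which section a site follows.

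The effect on DLT classification is a secondary and narrow possibility. One patient could change a Table 2 decision, but only if every condition in step 4 is met. The number of patients affected cannot be derived and is assumed to be small. The point deserves correction because it concerns safety and is cheap to resolve; no large effect on the trial's results has been shown. Nothing here says which clinical rule is right.

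**What to change.** Reconcile Section 9.2, the QTcF row of Table 7, Section 9.4.3 and Appendix F. State in 9.4.3 and Appendix F whether replacement for a documented deficiency falls inside or outside the prohibition, and make 9.2 and Table 7 agree with that statement. Then check that the Table 3 exception for oral supplementation is consistent with it. Both the clinical choice and the content of the DLT rule are for the sponsor.

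While editing, align the appendix letters: the prohibited list is headed Appendix F in the body but is Appendix E in the list in Section 20.0.

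The cost is a sentence in 9.4.3 and Appendix F, matching wording in 9.2 and Table 7, and a check of one line in Table 3. No procedures, visits or patients are added.
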